#### Analysis

For appointing non-inferiority, both the ITT and PP will be performed and both should attain to the predetermined non-inferiority margin (the one-sided 98.65% CI upper bound of the difference in proportions not exceeding 17.5%). For superiority (p<0.027), the ITT analysis will be considered as the primary analysis and the PP as a supportive analysis. For secondary outcome measures, solely the ITT analysis will be performed.

#### **Co-primary outcomes**

#### Pain

Pain will be measured by the NRS score (0–10 scale, 0 meaning "no pain" and 10 meaning "the worst pain imaginable") at 8 postoperative moments during POD 0 until 2. This outcome will be reported as the proportion of NRS measurements ≥4. The means of proportions per group will be reported with 95% CI. The upper limits of the 98.65% one-sided CI of differences in means of proportions for PVB versus TEA, respectively ICNB versus TEA, will be used to test for non-inferiority in the ITT as well as the PP analysis, represented in Figure 2 (2A and 2B).

#### Quality of recovery

QoR will be measured with the QoR-15 questionnaire at POD 1 and 2, and reported as the mean of these two values (Figure 2C). This outcome will be expressed as a discrete variable (minimum 0, maximum 150). Comparisons to test superiority will be made for the TEA versus PVB group and the TEA versus ICNB group. Superiority in terms of QoR is defined as a statistically significant higher mean score (p<0.027).

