Non-inferiority for pain is obtained only if the upper limit of the 98.65% one-sided confidence interval (CI) of the differences of mean proportion of NRS  $\geq$ 4 between the PVB versus TEA and ICNB versus TEA remains below the predetermined absolute margin of 17.5% in the intention-to-treat (ITT) analysis as well as in the per-protocol (PP) analysis. This non-inferiority margin is based on data from a previous pilot study, in which the proportion of pain scores  $\geq$  4 in a group of patients receiving TEA was 17.57% (SD 19.57) and in patients receiving continuous locoregional analgesia 21.21% (SD 23.33). Since the baseline of 17.57% of moments of pain in the control group is low, we accept an absolute margin of 17.5% from a clinical point of view. This margin of non-inferiority, accepting more moments of pain in the intervention techniques as compared to the control group, is justifiable in combination with superiority regarding QoR. Superiority regarding QoR is defined as a significantly higher mean score during POD 1 and POD 2 (p < 0.027) in the ITT analysis. Taking the mean QoR score during POD 1 and POD 2 is a simplifying improvement of the original superiority definition in the published study protocol (1) without affecting the sample size calculation.

Secondary outcomes are: 1) pain scores during rest and mobilization at the recovery room, in the evening of the day of operation, and in the morning, afternoon and evening on POD 1 until POD 3, and at 2-3 weeks follow-up; 2) proportion of NRS scores ≥4 during mobilization during POD 0 until 2; 3) QoR-15 at POD 0, POD 3 and 2-3 weeks follow-up; 4) cumulative use of opioids and analgesics at POD 0 until 3 and the plain use of opioids at 2-3 weeks follow-up; 5) postoperative complications until POD 30; 6) hospitalisation; 7) patient satisfaction at POD 0 until 3; 8) time to removal of the chest tube; 9) time of an indwelling urinary catheter; 10) degree of mobility at POD 0 until 3 and 11) cost-effectiveness analysis (separate analysis).

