#### Pain scores during rest and mobilisation

Pain scores in rest and during mobilisation will be registered at: baseline (pre-operatively); at the recovery room and in the evening of POD 0; in the morning, afternoon, and evening of POD 1-3 and at the follow-up appointment, generating 13 moments in which the pain scores are prospectively measured. Since pain scores are repeated measurements from the same patient, they are likely to be correlated and we cannot assume independency. As we expect the effect of analgesia is patient-specific and will therefore vary substantially from patient to patient, a linear mixed model will be used (Figure 3a). This analysis will lead to a more precise estimate of the trend in pain scores and how this outcome changes over time per analgesic technique. The model will include random intercepts, and baseline scores, time of the measurement and treatment group as fixed effects. The

linear mixed model will accommodate unbalanced data patterns by assuming missing data at random and use all available observations and patients in the analysis (10). We will apply the covariance matrix that fits best according to Akaike's Information Criterion (AIC) (11).

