#### QoR-15

The QoR-15 score ranges from 0-150 and will be expressed as a discrete outcome. Repeated measurements of QoR measured by the QoR-15 questionnaire taken at baseline (preoperative), from POD 0 until POD 3 and at follow-up will be analysed by a linear mixed model to depict the trend over time between the different analgesic techniques (Figure 3b).

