#### Patient replacement and missing data

In the sample size calculation, we have considered 12.6% extra inclusions due to drop-outs after conversions to thoracotomy (late exclusion). Since this percentage is appropriately represented by data from the Dutch Clinical Audit database from 2017, we do not expect further patient

replacement. Clinical data management is performed by independent professional data managers from the Dutch Comprehensive Cancer Centre. Once inclusions are complete, careful inspection of the data will take place. The mechanism causing data to be missing, whether it is (completely) at random or not at random, will guide the study group to apply analytical methods to amend missing data.

The incidence of missing data is partially limited by study design where minimum numbers of measurements suffice to generate an outcome value. For our non-inferiority research question regarding pain, complete cases include patients with at least 3 NRS measurements during POD 0 until 2 or a LOS  $\leq$  2 days, to allow detection of curvilinear pain patterns over time for reliable imputation. The cut-off for LOS  $\leq$  2 days is established due to the expectation that patients who have been discharged from the hospital have a NRS score  $\leq$  4 (standard of care). For our superiority question regarding QoR, complete cases include patients with at least one QoR-score during POD 0 until 2.

In case of remaining patients with lacking outcome data below 5% of the study size (14), the baseline Table 1 will be reproduced for patients intended to be included in the analysis as complete cases and added to the supplementary material (15). Imbalances in covariate distributions across groups derived from observed SMDs in this table, will be assessed from a clinical perspective for potential bias in prognosis and adjusted for in a primary analysis based on complete cases.

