# Appendix A. Overview statistical test per outcome

Outcome	Planned statistical test to compare
	randomization groups (each intervention versus
	control)
Baseline characteristics	None*
Primary outcome	
% NRS ≥ 4 POD 0-2 (at rest)	Non-inferiority, upper limit 98.6% CI <17.5%
Mean QoR-15 POD 1-2	Unpaired t-test or Mann-Whitney U-test
Secondary outcomes	
% NRS $\geq$ 4 POD 0-2 (mobilization)	Unpaired t-test or Mann-Whitney U-test
% NRS $\geq$ 4 baseline, POD 0-3 and follow-up (at rest)	Linear mixed model
% NRS $\geq$ 4 baseline, POD 0-3 and follow-up	Linear mixed model
(mobilization)	
QoR-15 at baseline, POD 0-3 and follow-up	Linear mixed model
Cumulative use of analgesics POD 0-3	Unpaired t-test or Mann-Whitney U-test
Cumulative use of opioids POD 0-3	Unpaired t-test or Mann-Whitney U-test
Cumulative use of analgesics (including opioids) at follow-up	Unpaired t-test or Mann-Whitney U-test
Postoperative complications	Mantel-Haenszel chi-squared test or Fisher's
	exact test
Length of hospitalization	Mann-Whitney U-test
Patient satisfaction	Mantel-Haenszel chi-squared test or Fisher's
	exact test
Presence of chest drain	Unpaired t-test or Mann-Whitney U-test
Presence of urinary catheter	Unpaired t-test or Mann-Whitney U-test
Degree of mobility	Mantel-Haenszel chi-squared test or Fisher's exact test

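### The QoR co-primary is a POD 1–2 mean, but a patient with one score counts as complete; on the natural reading one-day scores are compared with two-day means, which can bias the arm difference in either direction

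*SAP*

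**What the plan says.** - **Definition.** Under Quality of recovery: "QoR will be measured with the QoR-15 questionnaire at POD 1 and 2, and reported as the mean of these two values". The Summary of the study protocol agrees: "Superiority regarding QoR is defined as a significantly higher mean score during POD 1 and POD 2 (p < 0.027) in the ITT analysis".
- **Completeness rule.** Under Patient replacement and missing data, the SAP explains that missingness is limited because "minimum numbers of measurements suffice to generate an outcome value". For QoR, "complete cases include patients with at least one QoR-score during POD 0 until 2".
- **POD 0.** The window of that rule includes POD 0, although the POD 0 score is a secondary outcome: "3) QoR-15 at POD 0, POD 3 and 2-3 weeks follow-up".
- **Test.** Appendix A gives "Unpaired t-test or Mann-Whitney U-test" for the mean QoR-15 over POD 1–2.
- **Mixed model.** The SAP plans one for QoR-15, as a secondary analysis only: scores at baseline, "from POD 0 until POD 3 and at follow-up will be analysed by a linear mixed model".
- **Incomplete endpoints.** The section on protocol violation, adherence and deviation says that incomplete primary or secondary endpoints are protocol deviations and are treated as missing data. The steps in the missing-data section (reproduced baseline table, 5% threshold, imputation, weighting) apply to the patients who remain after the complete cases have been set apart.

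**The concern.** The definition needs two scores, while the completeness rule is satisfied by one. A patient with only a POD 1 or only a POD 2 score is complete and is expected to yield an outcome value, but no rule derives that value. The evident choice is the available score, and the test then treats it as equivalent to a two-day mean.

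If QoR differs between the two days and the arms differ in how many patients have only one of them, part of the arm difference reflects which days were measured rather than which technique was used. QoR carries the superiority claim and is the co-primary with the lower planned power (90%, against 99% for pain). The SAP also justifies its 17.5% pain margin by the expected gain in QoR. The error can cost power or create a false gain, depending on which arm has more one-day patients and on the direction of change.

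**Working it through.** **1. Does another section close the gap?** The sections can be followed in order for a patient with a POD 1 score only.
- Protocol violation, adherence and deviation: the endpoint is incomplete, so it is handled as missing data.
- Patient replacement and missing data: the patient has one score in the window, so is a complete case and is not among the remaining patients on whom the later steps act.
- Appendix A: one value per patient enters a t-test or Mann-Whitney test.

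The first section sends the patient to the second, and the second classes the patient as complete. The two need reconciling, and neither fixes the value to be used.

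**2. Size of the bias if the available score is used.** Let f be the share of POD 1-only patients in an arm, and D the POD 2 minus POD 1 change, taken as equal in both arms. A POD 1-only patient is scored D/2 away from the two-day mean, so

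shift in (experimental − TEA) = −(f_exp − f_TEA) × D/2.

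POD 2-only patients produce the mirror image. A simulation of 200,000 patients per arm, with D = 10 points, an assumed SD of 20 and POD 1-only shares of 25% against 5%, should give −0.20 × 10/2 = −1.0 point. It gave −1.02 with one-day status at random and −0.99 when better-recovering patients were the ones with POD 1 only. The true difference was zero. With D = 0 there was no shift.

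**3. Scale for the power figures.** The SAP gives 150 per arm, 12.6% drop-out, 90% power and two-sided alpha 0.027. It does not state the QoR effect size or SD, so the sample size itself cannot be reproduced; the effect that it implies can be solved for.
- Evaluable per arm: 150 × 0.874 = 131.1, taken as 131. Conversely, 131/0.874 rounds up to 150.
- SE = √(2/131) = 0.1236 SD.
- Effect for 90% power: (2.2115 + 1.2816) × 0.1236 = 0.4316 SD.

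**4. Range.** The share differences and day changes below are assumptions; the SAP gives neither. With bias b = (share difference) × (change)/2, in SD units and with scores rising:
- power, if the experimental arm has more POD 1-only patients: Φ((0.4316 − b)/0.1236 − 2.2115);
- false-positive rate in favour of the experimental arm, if TEA has more: Φ(b/0.1236 − 2.2115), which is 1.35% at b = 0.

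| Share difference | Change POD 1→2 | b (SD) | b/SE | Power | False-positive rate |
|---|---|---|---|---|---|
| 5 points | 0.25 SD | 0.006 | 0.05 | 89% | 1.5% |
| 10 points | 0.4 SD | 0.02 | 0.16 | 87% | 2.0% |
| 20 points | 0.4 SD | 0.04 | 0.32 | 83% | 3.0% |
| 20 points | 0.6 SD | 0.06 | 0.49 | 79% | 4.2% |

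The first row corresponds to a 5-point change on the QoR-15 if the SD is 20. If scores fall from POD 1 to POD 2, the two right-hand columns exchange arms. With equal shares or no change, b = 0.

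**The case against.** **The derivation is unspecified, not wrong.** The SAP does not say that the single score is used unaltered. It justifies the parallel minimum for pain as allowing reliable imputation, and it says that incomplete endpoints are handled as missing data. This stands in part: use of the single score is an inference. It is still the natural one, because the SAP says the minimum number of measurements is enough to produce an outcome value, the imputation remark belongs to the pain rule, and the later steps pass over patients classed as complete.

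**Direction.** A reader might infer that an arm with more POD 1-only patients is necessarily scored too low. The SAP does not support that. It gives no POD 1 to POD 2 change, and it has continuous analgesia provisionally stopped at POD 2 in TEA and PVB, so the change might even differ by arm.

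**Early discharge.** A reader might also infer that the bias penalises the technique that gets patients home sooner. The clause on a stay of 2 days or less belongs to the pain rule, and the SAP does not say that QoR-15 collection stops at discharge. The SAP does hypothesise shorter hospitalisation with the alternative techniques, so unequal loss of POD 2 scores is possible, but it remains an assumption.

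**Proportion.** Small imbalances cost little, the larger losses need a 20-point share difference for which the SAP offers no basis, and the two-day mean was chosen deliberately as a simplification. All true. A single sentence fixing the derivation would remove the ambiguity; it would remove the bias only if that sentence did not let one day stand for two.

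**Conclusion.** The definition of the QoR co-primary and its completeness rule do not fit together, and no other section repairs this. On the natural reading, one-day scores are compared with two-day means. The resulting bias is half the share difference times the day change. It has no fixed direction and vanishes if the shares are equal or scores do not change.

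Its size cannot be known from the SAP. Over the assumed range it goes from negligible (power 89%) to moderate (79%), or to a false-positive rate of up to 4.2% instead of 1.35% if TEA has the larger POD 1-only share and scores rise. These figures assume 131 evaluable patients per arm, the effect implied by 90% power, a change common to both arms, and use of the available score. The point should be corrected before the final analysis. It does not show that the planned comparison is invalid.

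**What to change.** 1. **Quality of recovery and Appendix A.** Enter the POD 1 and POD 2 scores as two observations per patient in a mixed model with treatment, day and treatment-by-day and an unstructured covariance. Test the equal-weight average of the two daily contrasts at p<0.027 for PVB versus TEA and for ICNB versus TEA. With complete data this estimate equals the planned difference in two-day means.
2. **Patient replacement and missing data.** Reword the QoR rule to refer to POD 1 and POD 2 scores, with a one-score patient contributing that day only. A POD 0 score alone then no longer makes a patient complete for an outcome that does not include POD 0.
3. **Protocol violation, adherence and deviation.** Bring the sentence on incomplete endpoints into line with the reworded rule.

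The cost is SAP wording: no new data are needed, and a QoR-15 mixed model is already planned. The Mann-Whitney alternative no longer applies to this outcome. The model also relies on the other score being missing at random given the observed one. The SAP already accepts a missing-at-random assumption for its pain-score mixed model, which is meant to "use all available observations and patients in the analysis", and it is weaker than letting one day stand for both.

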#### Secondary outcomes

During hospital admission after surgery, all secondary outcomes will be measured from POD 0 until POD 3 and if applicable, until discharge from the hospital (e.g. duration of chest tube drainage). The follow-up outpatient clinic visit is at 2-4 weeks after surgery, according to local hospital protocols. Outcomes are collected up until 30 days after surgery, as described in the protocol. All secondary outcomes will be compared between TEA versus PVB and TEA versus ICNB in the ITT group and tested for statistical significance (p<0.027). The data will be presented as illustrated in Table 3.

#### Pain scores during rest and mobilisation

Pain scores in rest and during mobilisation will be registered at: baseline (pre-operatively); at the recovery room and in the evening of POD 0; in the morning, afternoon, and evening of POD 1-3 and at the follow-up appointment, generating 13 moments in which the pain scores are prospectively measured. Since pain scores are repeated measurements from the same patient, they are likely to be correlated and we cannot assume independency. As we expect the effect of analgesia is patient-specific and will therefore vary substantially from patient to patient, a linear mixed model will be used (Figure 3a). This analysis will lead to a more precise estimate of the trend in pain scores and how this outcome changes over time per analgesic technique. The model will include random intercepts, and baseline scores, time of the measurement and treatment group as fixed effects. The

linear mixed model will accommodate unbalanced data patterns by assuming missing data at random and use all available observations and patients in the analysis (10). We will apply the covariance matrix that fits best according to Akaike's Information Criterion (AIC) (11).

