#### Analysis principles and general considerations

Continuous data will be reported as means with standard deviation (SD) or confidence intervals (CI), or medians with interquartile range (IQR) and will be compared between groups using the unpaired t-test or Mann-Whitney U, depending on the distribution of the data. Equality of variances for TEA and PVB, respectively ICNB, will be assessed with Levene's test. Categorical data will be presented as counts and percentages and data will be compared using Mantel-Haenszel Chi-squared test. In case of zero cell counts and when pooling of categories is not opportune, the Fisher's exact test will be used (7,8). For all secondary outcome measures, the CI and/or p-values will be provided to express the level of statistical significance per outcome without additional correction for multiplicity (also p<0.027). An overview of the planned statistical tests per outcome measure for group comparisons can be found in the Supplemental material (Appendix A).

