#### Protocol violation, adherence and deviation

Protocol violation is defined as non-adherence to the eligibility criteria, randomization process and study procedures, dictating that all patients should participate voluntarily and undergo an anatomical lung resection by VATS and one of the analgesic techniques (TEA, PVB or ICNB).

Protocol adherence defines that control patients should proceed to PVB catheter placement in case TEA catheter placement was unsuccessful; in case PVB too was unsuccessful, then ICNB should be done. Participants receiving TEA or PVB should have a provisional stop of the continuous analgesia at POD 2 and patients receiving TEA should have opioids administered through the epidural continuous mixture. Accidental luxation of the TEA or PVB catheter after surgery will not be seen as nonadherence.

Although the use of ERATS guidelines for enhanced postoperative recovery were advised by the protocol, it is expected that the level of implementation of each aspect of ERATS differs per hospital, for example the strict use of dexamethasone and 5-HT3 receptor antagonists. In addition, the availability of specific local anaesthetics (e.g. bupivacaine or ropivacaine) may vary and induce small between-hospital differences. To ensure equal distribution of small differences in ERATS aspects, we used treatment centre as stratification factor. Incomplete primary or secondary endpoints are considered a protocol deviation and are handled as missing data.

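### The pain mixed model is meant to show each technique's time course, but its listed fixed effects contain no treatment-by-time term and so give parallel arm profiles

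*SAP*

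**What the plan says.** - **Outcome.** The Summary of the study protocol lists as its first secondary outcome "pain scores during rest and mobilization at the recovery room" and at the later moments up to POD 3 and follow-up.
- **Aim and model for pain.** The section on pain scores during rest and mobilisation counts 13 measurement moments, including the preoperative one. It says the analysis will show the trend and "how this outcome changes over time per analgesic technique". The model is then stated: "The model will include random intercepts, and baseline scores, time of the measurement and treatment group as fixed effects".
- **Role of AIC.** "We will apply the covariance matrix that fits best according to Akaike's Information Criterion (AIC"). This selects the covariance, not the mean structure.
- **QoR-15.** The repeated scores from baseline to follow-up "will be analysed by a linear mixed model to depict the trend over time between the different analgesic techniques". No fixed or random effects are listed.
- **Testing.** Under Secondary outcomes, each experimental arm is compared with TEA and "tested for statistical significance (p<0.027"). The general considerations add that this is done "without additional correction for multiplicity (also p<0.027").
- **Elsewhere.** Appendix A gives only the name of the method for these rows. The caption of Figure 3 promises a line for each technique but states no terms. Additional analyses covers regression of the co-primary outcomes and exploration by centre.

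**The concern.** The aim and the model stand next to each other in one paragraph and do not match. A model with main effects of time and treatment lets pain change over time and lets the arms differ in level. It does not let the change over time differ between arms, which is what the paragraph sets out to describe.

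A constant difference is a strong assumption in this trial. ICNB is a single-shot block, while the other two arms are continuous: "Participants receiving TEA or PVB should have a provisional stop of the continuous analgesia at POD 2". A difference that appears, fades or reverses over the first days is plausible, and the listed terms would report it as one blended number. If the interaction were added only at analysis, its form and the contrast tested would be chosen after the data had been seen.

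**Working it through.** **1. Moments (reproducing the SAP's count).** Baseline 1 + POD 0 2 + POD 1-3 3 × 3 = 9 + follow-up 1 = 13, as stated. With baseline score as a covariate, 12 post-baseline moments remain. QoR-15 has POD 0, 1, 2, 3 and follow-up = 5.

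**2. What the listed terms imply.** Write the mean for arm g at moment t as

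E(Y) = μ + β·baseline + τ(t) + γ(g).

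The PVB-TEA difference at any t is γ(PVB) − γ(TEA), and likewise for ICNB. Neither depends on t, whether time is categorical or linear. Random intercepts shift a patient's level and leave this unchanged. So does any covariance that AIC selects.

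**3. Parameter count (categorical time, an assumption, since the SAP does not say).**
- Pain, as listed: 1 intercept + 1 baseline + 11 time + 2 treatment = 15.
- Pain, interaction: (3 − 1) × (12 − 1) = 22 more, or 11 df per comparison with TEA.
- QoR-15, interaction: (3 − 1) × (5 − 1) = 8 more, or 4 df per comparison.
- If time were linear, the interaction would add 2.

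**4. What a constant difference reports when the true one is not constant (illustration).** Assume two arms, complete data and compound symmetry. The generalised least squares estimate of the constant effect then weights the 12 moments equally, at any correlation. A difference present only at k moments is reported at k/12 of its size:

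| True difference confined to | k | Share reported |
|---|---|---|
| POD 0 | 2 | 2/12 = 17% |
| POD 3 | 3 | 3/12 = 25% |
| POD 0-2 | 2 + 3 + 3 = 8 | 8/12 = 67% |

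**5. The shares depend on what is assumed.** The weights are V⁻¹1 / (1′V⁻¹1), where V is the within-patient covariance matrix. For a POD 0-2 difference with complete data:
- AR(1), equally spaced moments: 63% at correlation 0.6 and 60% at 0.8.
- AR(1), follow-up 56 steps out (assumed, about 19 days at three steps a day): 53% at 0.6 and 43% at 0.8.

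Missing POD 3 scores would change the shares again. The table in step 4 is therefore one worked case and not a range. It also follows that, with a non-constant difference, the average being estimated depends on which covariance AIC picks.

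**6. A case where the effects cancel (simulated, assumed values).** With 131 patients per arm and a true difference of +1.0 NRS at the first 5 moments and −0.71 at the other 7 (average 0), the additive model returned 0.10 (SE 0.14). With the interaction, the per-moment estimates were +0.91 to +1.38 early and −0.46 to −0.79 later; the likelihood-ratio chi-square was about 253 on 11 df.

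**The case against.** The strongest reply is that the SAP says what the model will include, not that it includes nothing else. The same paragraph promises change over time for each technique, and Figure 3 is to show a line for each. The interaction may be intended and simply unwritten, and the figure that might show this is not available. That much stands: a reader might infer that the SAP rules out an interaction, and it does not. But the sentence is the SAP's only statement of the mean structure, and AIC is applied to the covariance alone. An analyst who follows the text fits parallel profiles.

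A second reply is that the additive model still compares each experimental arm with TEA on average, which is all that the Secondary outcomes section requires. This is also right, and it limits the point to the time-course aim.

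A third is that the outcomes are secondary. A reader might infer that the non-inferiority or superiority conclusions are at risk. They are not: the co-primary analyses use the per-patient proportion of NRS scores ≥4 and the mean QoR-15 over POD 1 and 2, and neither uses these mixed models.

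**Conclusion.** The point holds as a mismatch between a stated aim and the stated model. With the listed terms, each comparison with TEA is one constant difference from the recovery room to follow-up, so change over time by technique can be neither estimated nor tested. For QoR-15 the same aim is stated with no model terms.

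The parallel-profile result is algebra and needs no assumption beyond fitting the terms as listed. The sizes 2/12, 3/12 and 8/12 rest on compound symmetry and complete data. The SAP gives no correlations and leaves the covariance to AIC, so a reader should not take them as bounds on how far a time-limited difference could be diluted.

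The consequence is confined to secondary outcomes. The change should be made before the final analysis, but it does not touch the sample size or the co-primary tests.

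**What to change.** **Pain scores during rest and mobilisation.** Add treatment group by time to the fixed effects, with time as categorical moments and baseline score as a covariate; keep the random intercept and the AIC choice of covariance. For TEA versus PVB and TEA versus ICNB, name the difference averaged over the 12 post-baseline moments as the comparison tested at p<0.027. Report the treatment-by-time test (11 df per comparison) and the per-moment differences with 97.3% CIs (1 − 0.027) as describing the time course. The averaged contrast has to stay, because the interaction test does not respond to a constant difference.

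**QoR-15.** State the same structure with its 5 post-baseline moments (4 df per comparison).

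**Baseline wording.** The QoR-15 section, the Figure 3 caption and Appendix A all place baseline in the analysed or displayed series. Make them agree with its use as a covariate.

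**Cost.** SAP wording only, with the same data and software: 22 extra parameters for pain in each model (rest and mobilisation) and 8 for QoR-15. Tests at p<0.027 number 2 comparisons × 2 conditions = 4 for pain and 2 for QoR-15, no more than one constant difference per comparison would give. Per-moment intervals are wider than the averaged one. For example, under compound symmetry with an assumed correlation of 0.5, complete data and baseline adjustment, the SE ratio is √[0.75 / ((0.75 + 11 × 0.25)/12)] = 1.60.

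### The pain mixed model appears to use the pre-operative score both as a response and as a covariate, which would shrink a treatment main effect and its interval by about 8%

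*SAP*

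**What the plan says.** The section on pain scores during rest and mobilisation lists the times of registration as "baseline (pre-operatively); at the recovery room and in the evening of POD 0", then "in the morning, afternoon, and evening of POD 1-3 and at the follow-up appointment", and describes this as "generating 13 moments in which the pain scores are prospectively measured". It specifies the linear mixed model with the sentence "The model will include random intercepts, and baseline scores, time of the measurement and treatment group as fixed effects". No treatment-by-time term is named. The model is to "use all available observations and patients in the analysis", and the covariance matrix is chosen by AIC. The stated aim is to show how pain develops over time under each technique.

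Appendix A assigns a linear mixed model to the rest and mobilisation pain rows, each labelled as running from baseline through POD 0-3 to follow-up. The Figure 3a caption gives the mixed model the same range.

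The summary of the study protocol defines the outcome differently. Its first secondary outcome begins "1) pain scores during rest and mobilization at the recovery room" and names no pre-operative score.

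For QoR-15, repeated measurements "taken at baseline (preoperative), from POD 0 until POD 3 and at follow-up will be analysed by a linear mixed model", and Appendix A repeats the range as "QoR-15 at baseline, POD 0-3 and follow-up". Neither place lists fixed effects for that model.

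**The concern.** A pre-operative score cannot respond to an analgesic technique that has not yet been given. If it is a row of the response, the arm effect at that row is zero. If the same score is also a covariate, that row is predicted from itself. A treatment main effect then averages the postoperative difference with a structural zero, so both the estimate and its interval move toward no difference.

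The analysis principles promise confidence intervals and/or p-values for the secondary outcomes, and the secondary outcomes section tests each comparison at p<0.027, so a reported effect size could be affected. In addition, two statisticians working from this SAP could fit different response sets, one with 13 moments and one with 12.

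**Working it through.** **Count of moments** (section on pain scores during rest and mobilisation)

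- Pre-operative: 1
- POD 0, recovery room and evening: 2
- POD 1-3, three per day: 3 × 3 = 9
- Follow-up: 1

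1 + 2 + 9 + 1 = 13, which reproduces the SAP's figure. Without the pre-operative score it is 2 + 9 + 1 = 12, the set defined in the summary of the study protocol.

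**Effect on the treatment coefficient.** Take the listed fixed effects (baseline b, time, treatment g), random intercepts and complete data. The treatment coefficient is then the coefficient of g when each patient's mean over the modelled moments is regressed on b and g. With 13 moments that mean is

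(12 × postoperative mean + b) / 13.

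Regressing b on b and g gives a coefficient of 0 for g. Hence

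coefficient (13 moments) = 12/13 × coefficient (12 moments) = 0.923 × coefficient (12 moments).

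The shrinkage is 1 − 0.923 = 7.7%. The residual from the b part is also zero, so the standard error shrinks by the same factor and the test statistic stays put. The ratio between the two fits does not need a constant difference. Constancy is needed only to speak of one postoperative difference D that the model should return.

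**Check by simulation.** The assumptions, none of them from the SAP except the arm size, are:

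- 131 patients per arm, from 150 × (1 − 0.126) = 131
- true difference of 1 NRS point at every postoperative moment
- between-patient SD 1.2 and residual SD 1.5
- 40 runs, fitted by REML

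| Data | 13 moments | 12 moments | Ratio | Mean test statistic |
|---|---|---|---|---|
| Complete | 0.900 (SE 0.121) | 0.975 (SE 0.131) | 0.923 | 7.46 and 7.46 |
| 40% with in-hospital scores ending early | 0.908 (SE 0.121) | 1.000 (SE 0.134) | 0.908 | 7.48 and 7.49 |

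**Early discharge.** In the second row, 15% of patients stop after POD 1 (5 scores plus follow-up = 6) and 25% after POD 2 (8 plus follow-up = 9). A weighted average of the per-patient ratios agrees with the simulation:

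0.15 × 6/7 + 0.25 × 9/10 + 0.60 × 12/13 = 0.129 + 0.225 + 0.554 = 0.907.

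As limits, the ratio would be 6/7 = 0.857 if every patient had six postoperative scores, and 3/4 = 0.75 if every patient had three.

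**With a treatment-by-time term.** In one simulated data set the arm contrast at the pre-operative moment was 0.03, close to zero, and the postoperative contrasts were estimated separately. The dilution leaves the visit-wise contrasts.

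**The case against.** The sentence that specifies the model gives the baseline score one role only, as a fixed effect. Taken alone it is an ordinary baseline-adjusted model, and the 13 moments could describe data collection rather than the response. The summary of the study protocol supports that reading. Figure 3a is a display of hypothetical lines, and plotting baseline there is compatible with using it as a covariate. Appendix A is loosely labelled: its pain rows refer to the percentage of NRS scores of at least 4, while the text models pain scores. This stands to the extent that double use is not stated outright. It remains the most natural reading, because the count, the use of all available observations, Appendix A and the caption all point the same way, and nothing in the model section excludes the pre-operative row.

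The 12/13 figure is also conditional. A covariance matrix chosen by AIC would change the weight of the pre-operative row. The stated aim of following pain over time per technique suggests time-specific contrasts, which would be free of the dilution. Table 3 has no row for an overall mixed-model difference; the result is directed to Figure 3. All of this stands as a limit on size. However, the listed model has no interaction, and even with one the pre-operative row would still be regressed on itself.

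A reader might infer that the same double use is documented for QoR-15, with a larger dilution because there are fewer moments. The documents do not support this. The QoR-15 section puts the pre-operative value among the modelled measurements but names no fixed effects, and baseline as a response is legitimate when it is not also a covariate.

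**Conclusion.** The concern holds as a specification error or, at the least, an inconsistency in one secondary analysis. Read together, the pain section, Appendix A and the Figure 3a caption put the pre-operative score in the response while it is also a fixed effect; the outcome definition in the summary leaves it out. As written, a treatment main effect and its confidence interval are about 8% too close to zero. This assumes random intercepts, complete data, a constant postoperative difference that persists to follow-up, and no treatment-by-time term. Fewer postoperative scores make it somewhat worse (ratio 0.908 in the assumed early-discharge pattern).

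A reader might go on to infer that significance at p<0.027 is lost or gained. The calculation does not support that, since estimate and standard error shrink together. Nor do the co-primary analyses use this model, so neither the non-inferiority nor the superiority conclusion is touched.

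**What to change.** In the section on pain scores during rest and mobilisation, in Appendix A and in the Figure 3a caption, choose one of two specifications:

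- **Baseline as covariate only.** The response is the 12 postoperative moments, and the pre-operative score is a fixed effect.
- **Baseline as response only.** All 13 moments are in the response, the arms share a common mean at the pre-operative moment, and the baseline covariate is dropped.

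In either case, add a treatment-by-time term, because the stated aim needs it, and say which contrasts will be reported. Show baseline in Figure 3 descriptively. Bring the outcome definition in the summary of the study protocol and the other three places into agreement. Write out the QoR-15 model's fixed effects with the same specification.

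The covariate version needs a rule for patients without a pre-operative score. If that score is to be imputed, this must be reconciled with the baseline characteristics section, which rules out imputing missing baseline characteristics. The common-mean version avoids the question.

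The cost is SAP wording only; no new data are needed.
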